Appendix F: List of Strong Inducers and Inhibitors of CYP3A4

Cabozantinib is a CYP3A4 substrate (Section 7.3.1 Potential drug interactions with cabozantinib).

Chronic co-administration of cabozantinib with drugs known to be strong inducers of the CYP3A4 family may decrease cabozantinib concentrations and therefore should be avoided during treatment with cabozantinib. St. John's Wort (Hypericum perforatum) is also known to be an inducer of CYP3A4 and should be avoided.

Co-administration of cabozantinib with strong inhibitors of the CYP3A4 family may increase cabozantinib concentrations and should be avoided during treatment with cabozantinib.

Grapefruit, star fruit and Seville oranges may also increase plasma concentrations of cabozantinib and should be avoided during treatment with cabozantinib.

Strong Inhibitors of CYP3A4	Strong Inducers of CYPA4
Antivirals Boceprevir Cobicistat Conivaptan Danoprevir Dasabuvir Elvitegravir Indinavir Lopinavir Nelfinavir Ombitasvir Paritaprevir Ritonavir Saquevir Telaprevir Tipranavir Anti-Fungals Itraconazole Ketoconazole Posaconazole Voriconazole Antibiotics Clarithromycin Telithromycin Troleandomycin Conivaptan Diltiazem Grapefruit juice Idelalisib Nefazodone	Carbamazepine Efavirenz Enzalutamide Erythromycin Mitotane Modafinil Nevirapine Oxcarbazepine Phenytoin Rifampin St. John's Wort

This table is not all-inclusive. Please refer to the FDA website for the most updated lists of substrates, inducers, and inhibitors of selected CYP450 isozyme pathways:

<http://www.fda.gov/Drugs/DevelopmentApprovalProcess/DevelopmentResources/DrugInteractionsLabeling/ucm080499.htm>

Appendix G: Infusion-Related Reaction and Cytokine Release Syndrome Guidelines

Event	Management Guideline
Grade 1:^a Fever ^b with or without constitutional symptoms	
 • Immediately interrupt infusion. • Upon symptom resolution, wait for 30 minutes and then restart infusion at half the rate being given at the time of event onset. • If the infusion is tolerated at the reduced rate for 30 minutes, the infusion rate may be increased to the original rate. • If symptoms recur, discontinue infusion of this dose. • Administer symptomatic treatment,^c including maintenance of IV fluids for hydration. • In case of rapid decline or prolonged CRS (> 2 days) or in patients with significant symptoms and/or comorbidities, consider managing as per Grade 2. • For subsequent infusions, consider administration of oral premedication with antihistamines, anti-pyretics, and/or analgesics, and monitor closely for IRRs and/or CRS.
Grade 2:^a Fever ^b with hypotension not requiring vasopressors and/or Hypoxia requiring low-flow oxygen ^d by nasal cannula or blow-by	
 • Immediately interrupt infusion. • Upon symptom resolution, wait for 30 minutes and then restart infusion at half the rate being given at the time of event onset. • If symptoms recur, discontinue infusion of this dose. • Administer symptomatic treatment.^c • For hypotension, administer IV fluid bolus as needed. • Monitor cardiopulmonary and other organ function closely (in the ICU, if appropriate). Administer IV fluids as clinically indicated, and manage constitutional symptoms and organ toxicities as per institutional practice. • Rule out other inflammatory conditions that can mimic CRS (eg, sepsis). If no improvement within 24 hours, initiate workup and assess for signs and symptoms of HLH or MAS. • Consider IV corticosteroids (eg, methylprednisolone 2 mg/kg/day or dexamethasone 10 mg every 6 hours). • Consider anti-cytokine therapy.^c • Consider hospitalization until complete resolution of symptoms. If no improvement within 24 hours, manage as per Grade 3, that is, hospitalize patient (monitoring in the ICU is recommended), permanently discontinue atezolizumab, and contact Sponsor. • If symptoms resolve to Grade 1 or better for 3 consecutive days, the next dose of atezolizumab may be administered. For subsequent infusions, consider administration of oral premedication with antihistamines, anti-pyretics, and/or analgesics and monitor closely for IRRs and/or CRS. • If symptoms do not resolve to Grade 1 or better for 3 consecutive days, contact Sponsor.


Grade 3:^a
 
Fever^b with hypotension requiring a vasopressor (with or without vasopressin) and/or
 
Hypoxia requiring high-flow oxygen^d by nasal cannula, face mask, non-rebreather mask, or Venturi mask
	
 Permanently discontinue atezolizumab and contact Sponsor.^f Administer symptomatic treatment.^c For hypotension, administer IV fluid bolus and vasopressor as needed. Monitor cardiopulmonary and other organ function closely; monitoring in the ICU is recommended. Administer IV fluids as clinically indicated, and manage constitutional symptoms and organ toxicities as per institutional practice. Rule out other inflammatory conditions that can mimic CRS (eg, sepsis). If no improvement within 24 hours, initiate workup and assess for signs and symptoms of HLH or MAS. Administer IV corticosteroids (eg, methylprednisolone 2 mg/kg/day or dexamethasone 10 mg every 6 hours). Consider anti-cytokine therapy.^e Hospitalize patient until complete resolution of symptoms. If no improvement within 24 hours, manage as per Grade 4, that is, admit patient to ICU and initiate hemodynamic monitoring, mechanical ventilation, and/or IV fluids and vasopressors as needed; for patients who are refractory to anti-cytokine therapy, experimental treatments may be considered at the discretion of the investigator and in consultation with the Sponsor.

Grade 4:^a
 
Fever^b with hypotension requiring multiple vasopressors (excluding vasopressin) and/or
 
Hypoxia requiring oxygen by positive pressure (eg, CPAP, BiPAP, intubation and mechanical ventilation)
	
 Permanently discontinue atezolizumab and contact Sponsor.^f Administer symptomatic treatment.^c Admit patient to ICU and initiate hemodynamic monitoring, mechanical ventilation, and/or IV fluids and vasopressors as needed. Monitor other organ function closely. Manage constitutional symptoms and organ toxicities as per institutional practice. Rule out other inflammatory conditions that can mimic CRS (eg, sepsis). If no improvement within 24 hours, initiate workup and assess for signs and symptoms of HLH or MAS. Administer IV corticosteroids (eg, methylprednisolone 2 mg/kg/day or dexamethasone 10 mg every 6 hours). Consider anti-cytokine therapy.^e For patients who are refractory to anti-cytokine therapy, experimental treatments^g may be considered at the discretion of the investigator and in consultation with the Sponsor. Hospitalize patient until complete resolution of symptoms.

ASTCT, American Society for Transplantation and Cellular Therapy; BiPAP, bi-level positive airway pressure; CAR, chimeric antigen receptor; CPAP, continuous positive airway pressure; CRS, cytokine-release syndrome; CTCAE, Common Terminology Criteria for Adverse Events; eCRF, electronic Case Report Form; HLH, hemophagocytic lymphohistiocytosis; ICU, intensive care unit; IRR, infusion-related reaction; MAS, macrophage activation syndrome; NCCN, National Cancer Comprehensive Network; NCI, National Cancer Institute.

Note: The management guidelines have been adapted from NCCN guidelines for management of CAR T-cell-related toxicities (Version 2.2019).

^a Grading system for management guidelines is based on ASTCT consensus grading for CRS. NCI CTCAE (version 5.0) should be used when reporting severity of IRRs, CRS, or organ toxicities associated with CRS on the Adverse Event eCRF. Organ toxicities associated with CRS should not influence overall CRS grading.

^b Fever is defined as temperature $\geq 38^{\circ}\text{C}$ not attributable to any other cause. In patients who develop CRS and then receive anti-pyretic, anti-cytokine, or corticosteroid therapy, fever is no longer required when

subsequently determining event severity (grade). In this case, the grade is driven by the presence of hypotension and/or hypoxia.

- c Symptomatic treatment may include oral or IV antihistamines, anti-pyretics, analgesics, bronchodilators, and/or oxygen. For bronchospasm, urticaria, or dyspnea, additional treatment may be administered as per institutional practice.
- d Low flow is defined as oxygen delivered at ≤ 6 L/min, and high flow is defined as oxygen delivered at > 6 L/min.
- e There are case reports where anti-cytokine therapy has been used for treatment of CRS with immune checkpoint inhibitors (Rotz et al 2017; Adashek and Feldman 2019), but data are limited, and the role of such treatment in the setting of antibody-associated CRS has not been established.
- f Resumption of atezolizumab may be considered in patients who are deriving benefit and have fully recovered from the event. The decision to rechallenge with atezolizumab should be based on investigator's assessment of benefit-risk, and documented by both the investigator. The Medical Monitor is available to advise as needed. For subsequent infusions, administer oral premedication with antihistamines, anti-pyretics, and/or analgesics, and monitor closely for IRRs and/or CRS. Premedication with corticosteroids and extending the infusion time may also be considered after assessing the benefit-risk ratio.
- g Refer to Riegler et al (2019) for information on experimental treatments for CRS.

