
 • No premedication is permitted. • Vital signs (blood pressure, pulse, respiratory rate, and temperature) should be recorded within 60 min prior to the infusion. • Atezolizumab should be infused over 60 (\pm 15) min. • If clinically indicated, vital signs should be recorded during the infusion at 15, 30, 45, and 60 min (\pm 5 min for all time points) during the infusion and at 30 (\pm 10) min after the infusion. • Subjects should be informed about the possibility of delayed post-infusion symptoms and instructed to contact their study physician if they develop such symptoms. 	
 • If the subject experienced an IRR or CRS with any previous infusion, premedication with antihistamines, antipyretics, and/or analgesics may be administered for subsequent doses at the discretion of the investigator. • Vital signs should be recorded within 60 min prior to the infusion. • Atezolizumab should be infused over 30 (\pm 10) min if the previous infusion was tolerated without an IRR or CRS, or 60 (\pm 15) min if the subject experienced an IRR or CRS with the previous infusion. • If the subject experienced an IRR or CRS with the previous infusion or if clinically indicated, vital signs should be recorded during the infusion and at 30 (\pm 5) min after the infusion.

CRS, cytokine release syndrome; IRR, infusion-related reaction.

After the IV administration of the first dose of atezolizumab in the clinic, the subject will wait for at least 1 hour before taking cabozantinib. If the subject develops an infusion reaction or CRS, the oral administration of cabozantinib will be delayed or interrupted until the subject has recovered and the Investigator believes that it is safe to administer cabozantinib. For management of IRRs or CRS refer to [Appendix G](#).

If the first dose of atezolizumab cannot be given for any reason, no oral treatment with cabozantinib is to be initiated.

Sorafenib:

On the first day subjects are to fast (with the exception of water) for at least 2 hours before receiving sorafenib. After the 2-hour fast, the subject are to take the 400 mg oral dose of sorafenib with a glass of water in the clinic with no food intake for one more hour post-dose while under observation at the clinic to monitor for potential AEs. Subsequent doses will be self-administered at home ([Section 6.2.6](#)). Any unused study treatment must be returned to the study site for drug accountability and disposal.

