7. CONCOMITANT MEDICATIONS AND THERAPIES

7.1. Allowed Therapy

- Antiemetics and antidiarrheal medications are allowed prophylactically according to standard clinical practice if clinically indicated.
- Granulocyte colony-stimulating factors (G-CSF or GM-CSF) are allowed if used per clinical guidelines (eg, ASCO or ESMO guidelines).
- Bisphosphonates can be used per standard of care if the benefit outweighs the risk per the Investigator's discretion ([Section 6.6.2.1.8](#)).

Note: osteonecrosis of the jaw has been reported in subjects using bisphosphonates. Oral examinations are recommended at screening to determine eligibility and periodically during the study. In addition, subjects should be advised regarding oral hygiene practice and to quickly report symptoms to the Investigator. Frequent monitoring for potentially overlapping toxicities with study treatment is recommended.

- Transfusions and hormone replacement should be utilized as indicated by standard clinical practice.
- Inhaled, intranasal, intra-articular, or topical corticosteroids are allowed if minimal systemic absorption. Systemic corticosteroids are allowed for control of infusion reactions or irAEs and must be tapered over ≥ 1 month to a dose level ≤ 10 mg/day of prednisone equivalent before next atezolizumab administration. Prophylactic steroid treatment for subjects with contrast allergies prior to tumor imaging is allowed, and short term treatment with systemic corticosteroids for acute medical conditions (eg, exacerbation of chronic obstructive pulmonary disease [COPD]) is allowed if clinically indicated.
- Individualized anticoagulation therapy with heparin is allowed if it can be provided safely and effectively under the following circumstances:
 - *Low dose LMWH for prophylactic use* are allowed if clinically indicated and the benefit outweighs the risk per the investigator's discretion.
 - *Therapeutic doses of LMWH after first dose of study treatment* are allowed if clinically indicated (eg, for the treatment of DVT), and the benefit outweighs the risk per the

investigator's discretion. For management of thromboembolic complications while on study, refer to [Section 6.6.2.1.4](#).

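### After a steroid-treated Grade 2 infusion reaction or CRS, Appendix G permits the next atezolizumab dose without the taper of at least one month that Section 7.1 requires

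*Protocol*

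**What the plan says.** **Appendix G.** Protocol Sections 6.2.4 and 6.6.2.2.1 send sites to Appendix G for managing IRR and CRS. Its Grade 2 row asks the investigator to consider intravenous corticosteroids. The same row gives the condition for continuing: "If symptoms resolve to Grade 1 or better for 3 consecutive days, the next dose of atezolizumab may be administered". Neither the row nor the footnotes mention a taper or refer to Section 7.1.

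**Table 10 (Section 6.6.1).** Grade 2 IRR and CRS are among the events for which atezolizumab is delayed and may resume once the event is back to Grade 0-1. That row has no taper either.

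**Section 7.1.** This section is mandatory and names the event: "Systemic corticosteroids are allowed for control of infusion reactions or irAEs and must be tapered over ≥ 1 month", down to a level no higher than "10 mg/day of prednisone equivalent before next atezolizumab administration". Section 6.6.1 has the same rule for steroids started for immune-related adverse events (irAEs), and Table 31 in Section 8.3 classes IRR and CRS as irAEs.

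**Premedication.** Footnote f of Appendix G says: "Premedication with corticosteroids and extending the infusion time may also be considered after assessing the benefit-risk ratio". It is attached to permanent discontinuation in the Grade 3 and Grade 4 rows and concerns rechallenge. The Grade 2 row says only: "consider administration of oral premedication with antihistamines, anti-pyretics, and/or analgesics and monitor closely for IRRs and/or CRS". Table 6 likewise says: "premedication with antihistamines, antipyretics, and/or analgesics may be administered for subsequent doses". The only preventive steroid use that Section 7.1 lists is for contrast allergy before imaging. Section 7.2 prohibits immunosuppressive steroid doses apart from the exceptions in Section 7.1.

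**The concern.** A site treating a Grade 2 reaction will open Appendix G, because that is where the protocol sends it. If it gives steroids and then follows the row as written, it can dose on schedule and break a mandatory rule elsewhere. The layout makes this more likely. Tables 15 to 19, 21, 23, 24, 26 and 28, which allow atezolizumab to resume after other events, carry a footnote with the taper rule. Appendix G does not, so a site could reasonably conclude that infusion reactions are exempt, although Section 7.1 expressly includes them.

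The rule governs re-exposure after a reaction that, at Grade 2, involves hypotension or hypoxia. At about 250 sites in an open-label trial, the timing of atezolizumab and the steroid level at the next infusion would depend on which section a site read, and only in the experimental arm. Avoidable deviations would follow.

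**Working it through.** The plan has no figure to reproduce. The check compares time intervals and then sets the passages side by side.

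**Inputs**
- Planned interval: 21 days, plus or minus 2 (Protocol Section 6.2.4).
- Minimum spacing: 19 days (Protocol Section 5.2).
- Minimum taper: 1 month (Protocol Section 7.1). The SAP's General Conventions take a month as 30.4375 days. That is an analysis convention, used here only to express the taper in days.
- Onset of an infusion reaction: within 24 hours of the infusion (Protocol Section 6.6.2.2.1). The earliest start of a taper is therefore about the day of the infusion.

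**Dosing interval**
- Earliest: 21 − 2 = 19 days.
- Latest: 21 + 2 = 23 days.

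**Shortfall if the taper starts on the infusion day and lasts exactly one month**
- Against day 23: 30.4375 − 23 = 7.4 days.
- Against day 21: 30.4375 − 21 = 9.4 days.
- Against day 19: 30.4375 − 19 = 11.4 days.

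These are minimum values, since a later start or a longer taper adds to them day for day. The result does not hinge on the SAP convention, because any calendar month is longer than 23 days. The three-day symptom condition does not mean dosing on day 3, because the 19-day spacing still applies. The conflict is about the next scheduled dose.

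**Three situations after a Grade 2 reaction**
- *No systemic steroids given.* Appendix G permits the next dose and the Section 7.1 taper is not triggered. There is no conflict.
- *Steroids given, next dose on schedule.* Appendix G and Table 10 permit it. Section 7.1 forbids it, and so does Section 6.6.1 if IRR and CRS are irAEs as in Table 31.
- *Steroids given, next dose after the taper.* Every passage is satisfied.

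**Premedication.** The Appendix G Grade 2 row and Table 6 agree, and neither lists corticosteroids. Footnote f adds them for rechallenge after Grade 3 or 4 events. Section 7.1 does not list that use, and at immunosuppressive doses Section 7.2 would exclude it.

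**The case against.** The strongest reply is that the two conditions are cumulative. Section 7.1 says the taper is mandatory, while Appendix G only says that the dose may be given. Elsewhere the protocol stacks a symptom criterion and a taper, as in Tables 15 and 16. Table 10 repeats the taper in none of its rows, so silence in one row need not waive a general rule. On this view Appendix G lacks a cross-reference and states no opposing rule. The reading is available and satisfies every passage. But Appendix G does not state it, and the missing footnote points the other way.

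The reply does defeat several stronger readings that a reader might infer:
- *The Appendix G permission is empty.* It is not. Steroids at Grade 2 are only to be considered, and the permission operates in full when none are given.
- *Either course is a deviation.* Waiting for the taper breaches no permission, and Section 6.6.1 allows interruption of atezolizumab for adverse events at the investigator's discretion. Only on-schedule dosing after steroids breaches a passage.
- *A whole cycle is lost.* Doses may be delayed, and the minimum delay is about 9 days past day 21.
- *Steroid premedication is part of the Grade 2 conflict, and the taper rule cannot accommodate it.* Footnote f applies only to rechallenge after Grade 3 or 4 events. The taper in Section 7.1 is worded for steroids that control a reaction, and Table 6 does not say that its list is exclusive. What remains is that Section 7.1 does not list this use and Section 7.2 would exclude it at immunosuppressive doses.

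**Conclusion.** The inconsistency is real but limited. It arises for subjects in the experimental arm who receive systemic steroids for a Grade 2 IRR or CRS. For them, following Appendix G on schedule breaches Section 7.1, and following Section 7.1 delays the dose by at least about 9 days past the 21-day slot (7 to 11 days across the permitted interval). This assumes that the taper starts on the infusion day and lasts exactly one month. The steroid premedication gap in footnote f is a separate and narrower point.

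The documents give neither the rate of such reactions nor the share treated with steroids, so no count is offered.

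A reader might infer a threat to the primary analyses. The documents do not support that: in the SAP the primary PFS and OS estimands apply irrespective of whether the assigned treatment was given. The visible effect would be on conduct and exposure data. SAP Section 6.6 counts atezolizumab delays as dose holds and reports delays due to adverse events in bands that include 7 days or more. A 9-day delay counted from day 21 would enter that band at sites following Section 7.1 and would not arise at sites dosing on schedule. The wording should be corrected because it governs re-exposure after a reaction and the correction is cheap.

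**What to change.** The sponsor must reconcile Protocol Sections 6.6.1, 7.1 and 7.2, Table 6, Table 10 and Appendix G, including footnote f, on two questions:
- Does the taper apply to corticosteroids given for infusion reactions or CRS?
- Is corticosteroid premedication for atezolizumab permitted, and if so, in which situations?

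Appendix G should then cross-refer to the agreed rule, as the other resumption tables do through their footnotes. Which rule is right is for the sponsor and its clinical advisers. The cost is protocol wording and a communication to sites. No analysis or sample size changes.

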6.6. Safety Considerations

6.6.1. Management of AEs with Dose Reductions and/or Dose Interruptions

Subjects will be monitored for SAEs from the time of signing informed consent and for nonserious AEs from first dose of study treatment. Monitoring continues through 30 days (100 days for AESIs [Table 31] regardless of seriousness and for unrelated SAEs) after the date of the decision to permanently discontinue all study treatment (defined as the later of the date of the decision to discontinue all study treatment or the date of the last dose of any study treatment). Longer monitoring periods are required for related SAEs and certain other events as described in Section 8.4. Further details for follow-up and data collection requirements for AEs, SAEs, and AESIs are summarized in Appendix K. Subjects will be instructed to notify their physician immediately for any occurring AE. Causality assessment of AEs should include at minimum confounding factors such as disease and concomitant medications. Adverse event severity will be graded by the Investigator according to CTCAE v5.

The following should be taken into consideration in decisions regarding management for treatment-related side effects:

- Cabozantinib and atezolizumab have class-specific safety profiles based on their mechanism of action but may also cause AEs that overlap. For management of AEs in the experimental arm which can be clearly attributed to either cabozantinib or atezolizumab, independent dose modification for either agent is allowed.
 - Examples of VEGFR-TKI associated AEs caused by cabozantinib are hypertension and hand-foot syndrome.
 - Examples of AESIs caused by atezolizumab are pneumonitis and endocrinopathies.

For AEs without clear attribution to either study treatment, management of toxicity should include dose modifications of both agents per the discretion of the Investigator. Examples of overlapping AEs are diarrhea and transaminase increases.

- As a general approach all AEs should be managed with supportive care including both pharmacological and non-pharmacological treatments according to consensus management guidelines at the earliest signs of toxicity considered related to study treatment.
- Study treatment may be continued for mild AEs if appropriate supportive care has been initiated to ameliorate symptoms. Should this be ineffective and toxicities become

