Table 9: Dose Interruptions of Atezolizumab

Assigned dose	Dose Interruptions
1200-mg atezolizumab IV q3w	At any time to manage unacceptable AESIs

AESI, adverse events of special interest; q3w, once every 3 weeks;

Table 10: Dose Modifications for Atezolizumab-Associated Adverse Events

CTCAE v5 Grade	Recommended Management
Grade 1 immune-mediated myelitis*	Delay treatment with atezolizumab
Grade 1 pericarditis**	Treatment may be resumed in subjects following recovery to Grade 0-1
Grade 2 myocarditis	
Grade 1 ^a - 2 pneumonitis	* Continue atezolizumab unless symptoms worsen or do not improve.
Grade 2 nephritis	
Transaminases (ALT or AST):	** Withhold treatment with atezolizumab and conduct a detailed cardiac evaluation to determine the etiology and manage accordingly.
• Increases to between $> 3 \times$ ULN and $\leq 10 \times$ ULN (from baseline values \leq ULN), or	
• Increases to between $> 5 \times$ ULN and $\leq 10 \times$ ULN (from baseline values between $>$ ULN and $\leq 3 \times$ ULN), or	
• Increases to between $> 8 \times$ ULN and $\leq 10 \times$ ULN (from baseline values between $> 3 \times$ ULN and $\leq 5 \times$ ULN)	

CTCAE v5 Grade	Recommended Management
Grade 2 immune-mediated neuropathy (any cranial nerve disorder, including facial paresis, should be managed as per Grade 2 guidelines)***	Delay treatment with atezolizumab Treatment may be resumed in subjects following recovery to Grade 0-1.
Grade 2 or 3 diarrhea or colitis	
Grade 2 or 3 myositis	
Symptomatic adrenal insufficiency, hypothyroidism, or hyperthyroidism; Grade 2 or 3 hypophysitis; or Grade 3 or 4 hyperglycemia	*** For general immune-related neuropathy, if the event resolves to Grade 1 or better, resume atezolizumab. For facial paresis, if event resolves fully, resume atezolizumab; if event does not resolve fully while withholding atezolizumab, permanently discontinue atezolizumab.
Grade 2 ocular inflammatory toxicity	
Grade 2 or 3 pancreatitis or Grade 3 or 4 increases in amylase or lipase levels	
Grade 3 or 4 infection	
Grade 2 infusion-related reactions or cytokine release syndrome	
Grade 3 rash	
Suspected Stevens-Johnson syndrome or toxic epidermal necrolysis (any grade)	
Other Grade 2 or 3 atezolizumab-associated AEs	
Grade 2 - 4 immune-mediated myelitis	Permanently discontinue atezolizumab
Grade 3 or 4 immune-mediated neuropathy, including facial paresis	
Grade 2 - 4 myocarditis	
Grade 4 myositis and/or recurrent Grade 3 myositis	
Grade 3 or 4 pneumonitis	

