Grade 3 or 4 nephritis	
AST or ALT $> 10 \times$ ULN or total bilirubin $> 3 \times$ ULN	
Grade 4 diarrhea or colitis	
Grade 4 hypophysitis and/or recurrent hypophysitis	
Myasthenic syndrome/myasthenia gravis, Guillain-Barré or meningoencephalitis (all grades)	
Grade 3 or 4 ocular inflammatory toxicity	
Grade 4, or recurrent Grade 2 or 3, immune-mediated pancreatitis	

CTCAE v5 Grade	Recommended Management
Grade 3 or 4 infusion-related reactions or cytokine release syndrome	
Grade 4 rash	
Confirmed Stevens-Johnson syndrome or toxic epidermal necrolysis (any grade)	
Other Grade 4 or recurrent Grade 3 atezolizumab-associated AEs	Permanently discontinue atezolizumab

AE, adverse event; AESI, adverse events of special interest; ALT, alanine aminotransferase; AST, aspartate aminotransferase; irAE, immune-related adverse event; ULN, upper limit of normal.

Note: Additional information for atezolizumab dose modification criteria and treatment recommendations for irAEs, infusion reactions, and other AESIs are provided in [Section 6.6.2.2](#).

^a Consider interrupting atezolizumab for Grade 1 pneumonitis.

^b Resumption of atezolizumab may be considered in patients who are deriving benefit and have fully recovered from the immune-mediated event. The decision to re-challenge patients with atezolizumab should be based on investigator's assessment of benefit–risk and documented by the investigator. The Medical Monitor is available to advise as needed.

Sorafenib:

- The assigned dose for sorafenib is 400 mg twice daily.
- When dose reduction is necessary, the sorafenib dose may be reduced to 400 mg once daily (qd). If additional dose reduction is required, sorafenib may be reduced to a single 400 mg dose every other day (qod).

For additional details on management guidance of AEs refer to the most current sorafenib prescribing information appropriate to the respective site location.

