6.6.2.2.1. Infusion-Related Reactions and Cytokine Release Syndrome

IRRs are known to occur with the administration of monoclonal antibodies and have been reported with atezolizumab. These reactions, which are thought to be due to release of cytokines and/or other chemical mediators, occur within 24 hours of atezolizumab administration and are generally mild to moderate in severity.

CRS is defined as a supraphysiologic response following administration of any immune therapy that results in activation or engagement of endogenous or infused T cells and/or other immune effector cells. Symptoms can be progressive, always include fever at the onset, and may include hypotension, capillary leak (hypoxia), and end-organ dysfunction (Lee et al 2019). CRS has been well documented with chimeric antigen receptor T-cell therapies and bispecific T-cell engager antibody therapies but has also been reported with immunotherapies that target PD-1 or PD-L1 (Rotz et al 2017; Adashek and Feldman 2019), including atezolizumab.

No premedication is indicated for the first administration of atezolizumab. However, subjects who experience an IRR or CRS with atezolizumab may receive premedication with antihistamines, antipyretics, and/or analgesics (eg, acetaminophen) for subsequent infusions. Metamizole (dipyrone) is prohibited in treating atezolizumab-associated IRRs because of its potential for causing agranulocytosis.

There may be significant overlap in signs and symptoms of IRRs and CRS, and in recognition of the challenges in clinically distinguishing between the two, consolidated guidelines for medical management of IRRs and CRS are provided in [Appendix G](#).

Severe COVID-19 appears to be associated with a CRS involving the inflammatory cytokines IL-6, IL-10, IL-2, and IFN- γ (Merad and Martin 2020). If a patient develops suspected CRS during the study, a differential diagnosis should include COVID-19, which should be confirmed or refuted through assessment of exposure history, appropriate laboratory testing, and clinical or radiologic evaluations per investigator judgment. If a diagnosis of COVID-19 is confirmed, the disease should be managed as per local or institutional guidelines.

For subjects who develop COVID-19 while on study, the Investigator is to evaluate the overall risk-benefit ratio for the subject to determine whether holding study treatment(s) is in the best interest of the subject.

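### Table 10 and Appendix G both set atezolizumab delay, restart and permanent stop after infusion reactions or CRS, on different grading scales with no stated precedence; an infusion reaction without fever has no row in Appendix G, and the Grade 2 instructions differ

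*Protocol*

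**What the plan says.** **Table 10 (Protocol Section 6.6.1).** The section gives Table 10 as the place for atezolizumab dose-modification criteria for immune-related and other special-interest events, and for guidance on reinstatement. Table 31 (Section 8.3) lists infusion-related reactions and CRS among those events. The grade column is headed "CTCAE v5 Grade", which matches the section's general rule: "Adverse event severity will be graded by the Investigator according to CTCAE v5". The delay block contains "Grade 2 infusion-related reactions or cytokine release syndrome", with resumption after recovery to Grade 0-1. The permanent-discontinuation block contains "Grade 3 or 4 infusion-related reactions or cytokine release syndrome". The note under the table points to Section 6.6.2.2 for further information.

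**Section 6.6.2.2.1.** Because IRRs and CRS are hard to tell apart, "consolidated guidelines for medical management of IRRs and CRS are provided in" Appendix G. Section 6.2.4 makes the same referral for both. Section 6.6.2.2.1 describes CRS as always having fever at onset and sets no such condition for IRRs.

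**Appendix G.** It gives four graded rows with instructions on restarting the infusion, giving the next dose and permanent discontinuation. Footnote a says: "Grading system for management guidelines is based on ASTCT consensus grading for CRS". It then says: "NCI CTCAE (version 5.0) should be used when reporting severity of IRRs, CRS, or organ toxicities associated with CRS on the Adverse Event eCRF". Footnote c adds: "For bronchospasm, urticaria, or dyspnea, additional treatment may be administered as per institutional practice".

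**The concern.** Two parts of one protocol tell the investigator whether to continue, delay or permanently stop atezolizumab after the same type of event. They do so by grade numbers from different scales, without saying which number counts. Section 6.6.2.2.1 treats IRRs and CRS together, but the scale used in Appendix G was built for CRS and starts from fever. A reaction with bronchospasm or urticaria and no fever is therefore sent to a guideline that has no grade for it.

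At stake is consistent handling of a safety decision across approximately 250 sites, made at or soon after the infusion. There is also a small reporting consequence: the grade that led to a stop may not be the grade under which that stop is tabulated.

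**Working it through.** No sample size, power, alpha or event count is involved, so the check sets the passages side by side.

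**Step 1: which scale each place uses.** Table 10 uses CTCAE v5, by its column heading and the general rule in Section 6.6.1. Appendix G uses ASTCT CRS grading for management and CTCAE v5 for the eCRF, by footnote a.

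**Step 2: what each place instructs.**

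| Situation | Table 10 | Appendix G |
|---|---|---|
| Grade 2 on the table's own scale | Delay; may resume after recovery to Grade 0-1 | Interrupt; restart the same infusion at half rate 30 minutes after symptoms resolve; next dose after 3 consecutive days at Grade 1 or better |
| Grade 3 or 4 on the table's own scale | Permanently discontinue | Permanently discontinue |
| IRR that never had fever | Delay at Grade 2; permanently discontinue at Grade 3 or 4 | No row |

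**Step 3: whether the third line is a real gap.** All four Appendix G definitions begin with fever, which footnote b sets at 38 °C or more with no other cause. Footnote b drops the requirement only when severity is judged again in a patient who has already developed CRS and then received antipyretic, anti-cytokine or corticosteroid therapy. A reaction without fever at any time does not meet that exception. Footnote c names bronchospasm, urticaria and dyspnea, but only for symptomatic treatment; no restart or stop instruction follows.

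**Step 4: whether any text settles precedence.** Section 6.6.1 assigns dose modification and reinstatement to Table 10. The note under Table 10 offers Section 6.6.2.2 as a supplement, not as a replacement. Footnote a states which scale Appendix G uses and does not mention Table 10. No sentence ranks the two.

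**Step 5: effect on the analysis.** SAP Section 8.1 builds the summaries of adverse events leading to discontinuation from the action-taken field for each agent. Grade does not decide whether a discontinuation is counted. Grade does decide the column, because those tables are split by worst CTCAE severity. In SAP Section 8.3, the table of special-interest events leading to IV discontinuation has columns only from Grade 3 upward. If the sponsor's special-interest term list includes IRR/CRS, a stop made on an ASTCT Grade 3 but reported as CTCAE Grade 2 would have no column there.

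**The case against.** The strongest reply is that the protocol runs from general to specific. Table 10 is a summary, its note leads to Section 6.6.2.2, that section leads to Appendix G, and footnote a there separates managing from reporting. The Table 10 heading is not strict either, since the column also holds transaminase multiples of the upper limit of normal. On this view only one sentence on precedence is missing. This is a fair reading, but an inferred one. If Appendix G governs, an IRR without fever loses its continuation rule. If Table 10 governs, the Appendix G actions rest on a scale that does not decide them. Either way the text needs a change.

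A second reply is that the Grade 2 instructions are compatible: restart in Appendix G follows symptom resolution, which fits recovery to Grade 0-1. That narrows the difference. Section 5.2 requires doses to be at least 19 days apart, so the three-day condition matters only if symptoms last close to the next dose. It does not remove the difference over the interrupted infusion, where one place says delay and the other describes a restart the same day.

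A third reply is that Table 10 covers Grade 2-4 reactions without fever, and that Table 6 covers premedication, infusion time and vital signs after any IRR. This stands. A reader might infer that the two places flatly contradict each other for reactions without fever. They do not: one gives an instruction and the other is silent. It is a gap in the guideline to which sites are referred, filled only by Table 10.

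**Conclusion.** The point holds as an inconsistency in a safety rule with three parts: two scales with no stated precedence, no Appendix G row for an IRR without fever, and different Grade 2 wording. At Grade 3-4 the instruction is the same and only the scale differs.

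Two stronger readings are not supported:

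- A reader might infer that the same febrile reaction will often get different grades and so different actions. The CTCAE definitions of IRR and CRS are not in the documents, so how often the scales diverge cannot be determined from them.
- A reader might infer that discontinuation counts are distorted. They are not, because they come from the action-taken field. Only the severity column may change.

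The size is unquantified. The experimental arm is planned at 370 or more subjects, and subjects who cross over would also receive atezolizumab, but these are numbers exposed, not numbers affected. No incidence of IRR or CRS in this setting is given, and Section 6.6.2.2.1 describes IRRs as generally mild to moderate. No primary or secondary efficacy endpoint is touched. The conclusion rests on the protocol text alone; local prescribing information and the Investigator's Brochure, to which Section 6.6.2.2 also refers, were not available.

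**What to change.** Reconcile the passages:

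1. In the IRR/CRS rows of Table 10 and in Appendix G, state which grading scale governs the decision to delay, restart or permanently discontinue atezolizumab.
2. Make the Grade 2 instructions in the two places agree, covering both the interrupted infusion and the next dose.
3. State in Appendix G how an IRR without fever is handled, for example by cross-reference to the governing rule.

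The choice of scale and of clinical rule is for the sponsor. The cost is wording in Table 10 and Appendix G. CTCAE reporting on the eCRF and the SAP's counting of discontinuations can stay as they are.
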